4.1. Sample Size

This study will enroll up to 27 subjects (1 subject in Cohort 2 and 2 subjects in each of the other 6 cohorts with potential enrollment of approximately 2 additional subjects in any cohort).

The sample size for this study was not based on statistical considerations, but is considered sufficient to provide preliminary assessments of the safety and tolerability of SB-318 in subjects with MPS I, as well as biochemical changes related to the pathophysiology of MPS I. Subjects who prematurely discontinue the study prior to the 12 months of study follow-up (i.e., subjects who were enrolled but not dosed, were lost to follow-up, or discontinued prematurely for another reason) may be replaced at the discretion of Sangamo.

4.2. Analysis Set

4.2.1. Enrolled Set

The Enrolled set includes subjects who have signed the informed consent form and have met all inclusion and exclusion criteria.

4.2.2. Safety Set

The Safety set includes all subjects enrolled in the study and receive any portion of the SB-318 infusion.

All collected data used for table summaries will be based on Safety set unless otherwise specified.

5. Subject Disposition

5.1. Disposition

A disposition of subjects includes the number and percentage of subjects for the following categories: subjects who screen failed, subjects who were enrolled, subjects who received any portion of the SB-318 infusion, subjects who completed the study, and subjects who terminated early from the study. The disposition will be summarized by treatment cohort and overall. The percentages will be based on the number of subjects in each treatment cohort and overall. The reasons for early termination of study will also be summarized in the table.

Subject disposition data will be presented in a listing. A separate listing of reasons for screen failure will be provided. The number of screen fails and the screen criteria failed will be summarized in a table.

5.2. Protocol Deviations

Deviations from the protocol including violations of inclusion/exclusion criteria will be assessed as ‘significant’ in cooperation with the sponsor. Deviations will be defined prior to database lock. Protocol deviations will be presented in a listing and summarized by category. All COVID-19-related protocol deviations will be summarized by category and flagged in the corresponding listing.

6. Demographics and Baseline Characteristics

6.1. Demographics

The demographics will be summarized by treatment cohort and overall. The following variables will be included:

- Age (Years)
- Sex (Male, Female)
- Ethnicity (Hispanic or Latino, Not Hispanic or Latino)
- Race (African American, American Indian or Alaska Native, Asian, Native Hawaiian or Other Pacific Islander, White, Not Provided, or Other)
- Weight and Height at baseline prior to dosing

The demographics data will be presented in a listing as well.

6.2. Baseline Characteristics

6.2.1. Chest X-RAY

Chest X-Ray assessment will be performed at Screening visit only. Corresponding listing include clinically significant abnormal findings will be provided.

6.2.2. MPS I Gene Sequencing

Sample of MPS I gene sequencing will be collected at Screening visit only. The data will be presented in a listing.

6.2.3. Single-Nucleotide Polymorphism (SNP) Assay

Sample of SNP assay will be collected at Screening visit to identify polymorphisms in the ZFN-targeted region of the albumin locus. The data will be presented in a listing.

6.2.4. Viral Load

Testing for human immunodeficiency virus (HIV), hepatitis B virus (HBV), and hepatitis C virus (HCV) will be collected at Screening visit only. The data will be presented in a listing.

6.2.5. Neutralizing Antibodies to AAV2/6

The level of neutralizing antibodies to AAV2/6 will be collected at Screening visit only to assess the subject's pre-existing immune response to AAV2/6. Listing is provided to display the results.

6.3. Medical History

The number and percentage of subjects with a medical history will be summarized by treatment cohort and overall for each body system by system organ class (SOC) and preferred term (PT). Percentages will be calculated based on number of subjects for the Safety set. Corresponding listing will be provided.

MedDRA dictionary Version 23.0 will be used for reporting and will be described in the relevant table and listing footnotes.

7. Study Treatments

The 3 components of SB-318 (ZFN1, ZFN2, and IDUA Donor) will each be added to 200 mL of diluent and adjusted to 0.25% human serum albumin. Total infusion volumes will depend on subject's cohort assignment and body weight (kg). IV infusions will be administered while the subject is in the hospital or acute care facility. The subject will remain in the hospital or acute care facility for at least 24 hours after SB-318 infusion for observation and will be discharged when all AEs and vital signs (temperature, heart rate, respiratory rate, and blood pressure) are stable.

All infusion data including specific details will be presented in a listing.

8. Endpoint Analysis

The primary objective of this study is to evaluate the safety and tolerability of SB-318. All statistical summaries will be descriptive in nature (e.g., means, standard deviations, and percentages). All subjects who receive any portion of the SB-318 infusion will be included

in the analyses, even those who withdraw prematurely from the study. All results will be presented separately for each of the SB-318 dose levels.

8.1. Primary Endpoint Analysis

8.1.1. Adverse Events

A treatment-emergent adverse event (TEAE) is defined as any adverse event with an onset date on or after the date of the SB-318 infusion through the last study visit, whether or not it is considered causally related to the study drug.

Treatment Emergence:

Totally Missing Dates:

- If both the onset date and the end date are, then the adverse event is assumed to be treatment emergent.

Partially Missing Dates:

- If the onset date is missing and the non-missing end date is prior to the infusion date, then the AE is not considered treatment emergent.
- If the partial end date can be assumed to be prior to the infusion date (month and/or year before infusion date), then the AE is not considered treatment emergent.
- If the end date is after the infusion date or the partial end date can be assumed to be on or after the infusion date (based on month and/or year), then the AE is assumed to be treatment emergent.
- If the onset date is partial and can be assumed to be prior to the infusion date (based on the month and/or year) or the non-missing end date is prior to the infusion date then the AE is not considered treatment emergent.
- If the partial onset date can be assumed to be on or after the infusion date, then the AE is assumed to be treatment emergent.

All AEs will be coded according to the most recent version of the MedDRA. Severity will be categorized by toxicity grade according to the Common Terminology Criteria for Adverse Events (CTCAE) Version 4.03.

AEs not listed in the CTCAE version 4.03 will be evaluated by using the following criteria:

- Grade 1, Mild: Symptoms cause no or minimal interference with usual social and functional activities
- Grade 2, Moderate: Symptoms cause greater than minimal interference with usual social and functional activities
- Grade 3, Severe: Symptoms cause inability to perform usual social and functional activities

- Grade 4, Potentially Life-threatening: Symptoms cause inability to perform basic self-care functions OR medical or operative intervention indicated to prevent permanent impairment, persistent disability, or death
- Grade 5: Outcome of AE is death.

Incidence of Adverse Events

The incidence of AEs will be summarized in tables with count and percentage of subjects with AEs by system organ class (SOC) and preferred term (PT). Unless otherwise specified, at each level of SOC or preferred term, a subject with multiple events will only be counted once per SOC or preferred term. Percentages of subjects with AEs will be calculated out of the number of subjects in each summary cohort of the intent-to-treat set. Tables will be sorted by SOC alphabetically in overall group and PT in decreasing order on total frequency order.

The following categories of AE will be summarized:

- TEAEs
- Severity (CTCAE Grade 1, 2, 3, 4 and 5) of TEAEs
- TEAEs by relationship to study drug
- Grade 3 or greater TEAEs
- Serious TEAEs
- Grade 3 or greater Serious TEAEs
- Grade 3 or greater TEAE related to study treatment
- TEAEs leading to study discontinuation
- TEAEs leading to death

All AEs will be presented in data listings. TEAEs and SAEs will be flagged in the listings.

Severity of Adverse Events

All AEs will be summarized by maximum severity (CTCAE Grade 1, 2, 3, 4 and 5), SOC, and preferred term. At each level of SOC or preferred term, a subject with multiple events will only be counted once by the maximum severity per SOC or preferred term. No imputation will be done for missing severity. Adverse Events with missing severity will be presented in tables and listings as is.

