ERT Withdrawal	
Subjects who received SB-318 may no longer require weekly administration of ERT, and therefore may be considered for withdrawal of ERT (if applicable).
 
ERT withdrawal will be a controlled process, with additional safety monitoring to reduce potential risk to the subject, and is an optional part of the study.
 
ERT withdrawal may be initiated by the Principal Investigator after consultation with the Sponsor, and only in subjects who are willing and who meet all of the following criteria:
 

• are <math>\geq 12</math> weeks post-administration of SB-318;

• are medically stable and can tolerate temporary discontinuation of ERT at the judgement of the Principal Investigator; and

• agree to additional safety monitoring and clinical laboratory testing until the ERT Withdrawal Follow-Up visit (see Appendix 2).

 
ERT does not need to be restarted after the ERT Withdrawal Follow-Up visit. However, ERT may be re-initiated at any time based on clinical circumstances or at the judgement of the Principal Investigator.

Study Duration	
The duration of study participation will be approximately 39 months for each subject, divided into approximately 3 months for Screening followed by 36 months for treatment and study follow-up.
 
Upon completion of the study, subjects will be asked to participate in a separate Long-term Follow-Up (LTFU) Study to monitor the long-term safety of SB-318. To alleviate study burden, study subjects may participate in the LTFU Study after at least 12 months of follow-up in this study. Study participants who wish to enroll in the LTFU Study with less than 12 months of follow-up in this primary study may be considered on a case-by-case basis at the judgement of the Principal Investigator and after consultation with the Sponsor.

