**Figure 5. Schema of Study Visits.**

Upon completion of the study, subjects will be asked to participate in a separate Long-term Follow-Up (LTFU) Study to monitor the long-term safety of SB-318. To alleviate study burden, study subjects may participate in the LTFU Study after at least 12 months of follow-up in this

study. Study participants who wish to enroll in the LTFU Study with less than 12 months of follow-up in this primary study may be considered on a case-by-case basis at the judgement of the Principal Investigator and after consultation with the Sponsor.

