#### **6.9 Months 15, 18, 21, 24, 27, 30, 33, and 36/End of Study (+/-1 month)**

Subjects will be evaluated every 3 months in Years 2 and 3 after SB-318 infusion.

An End of Study (EOS) visit will be conducted at Month 36.

At the EOS visit, subjects will be asked to participate in the LTFU Study. Study subjects may participate in the LTFU Study after 12 months of follow-up in this study, in which case an EOS visit may be conducted anytime after Week 52 but before the next scheduled study visit. Study participants who wish to enroll in the LTFU Study with less than 12 months of follow-up in this primary study may be considered on a case-by-case basis at the judgement of the Principal Investigator and after consultation with the Sponsor. In these cases an EOS visit may be conducted anytime when transition to the LTFU study is imminent. Informed consent will be obtained prior to participating in the LTFU Study.

The following assessments and procedures will be performed unless otherwise stipulated:

- Review and record concomitant medications.
- Physical examination.
- Vital signs.
- Assessment of AEs.
- ERT administration log.
- JROM (at Months 18, 24, 30, and 36/EOS only).
- Neurologic cranial nerve exam and muscle strength testing of the upper extremities (at Months 18, 24, 30, and 36/EOS only).

- 12-lead ECG (at Months 18, 24, 30, and 36/EOS only).
- ECHO (at Months 24 and 36/EOS only).
- Clinical laboratory tests.
- Liver panel.
- Chimerism assay (at Month 36/EOS only; for post-HSCT subjects only)
- GAG testing in urine.
- IDUA / GAG testing in blood.
- Circulating AFP level (at Months 18, 24, 30, and 36/EOS only).
- PFTs (at Months 18, 24, 30, and 36/EOS only).
- 6MWT (at Months 18, 24, 30, and 36/EOS only).
- Visual acuity test and corneal clouding exam (at Months 24 and 36/EOS only).
- Neurocognitive abilities tests by WASI-II, WPPSI-IV, or BSID-III, and by VABS-II (at Months 18, 24, 30, and 36/EOS only).
- MRI of liver (at Months 18, 24, 30 and 36/EOS only).
- MRI of brain and cervical spine (at Months 24 and 36/EOS only).
- Immunogenicity assays (at Months 18 and 24 only).

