#### **10.2 Adverse Event Reporting Period**

AEs will be monitored continuously during the study from the time that the subject has provided written informed consent through the subject's last day of study participation. Subjects will be queried and events will be assessed at each clinic visit. A treatment-emergent AE (TEAE) is any AE with an onset from any time from administration of the study treatment through the last study visit, whether or not it is considered causally related to the study treatment.

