3.2. Study Endpoints

3.2.1. Primary Endpoints

The primary endpoint of this study is the incidence of treatment-emergent AE's (including SAEs).

Additional safety evaluation will be included:

- Routine hematology, chemistry and liver function laboratory tests, vital signs, physical exam, ECG, ECHO, and concomitant medications.
- Monitoring of chimerism in post-HSCT subjects.
- Cranial nerve exam and muscle strength testing.
- Serial alpha-fetoprotein (AFP) testing and magnetic resonance imaging (MRI) of liver to evaluate for liver mass.

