SYSTEM ORGAN CLASS #1	xx (xx.x)	xx	xx (xx.x)	xx	xx (xx.x)	xx
PREFERRED TERM #1	xx (xx.x)	xx	xx (xx.x)	xx	xx (xx.x)	xx
PREFERRED TERM #2	xx (xx.x)	xx	xx (xx.x)	xx	xx (xx.x)	xx
...		xx		xx		xx
SYSTEM ORGAN CLASS #2	xx (xx.x)	xx	xx (xx.x)	xx	xx (xx.x)	xx
PREFERRED TERM #1	xx (xx.x)	xx	xx (xx.x)	xx	xx (xx.x)	xx
PREFERRED TERM #2	xx (xx.x)	xx	xx (xx.x)	xx	xx (xx.x)	xx
...						
...						

n = number of subjects experiencing the event. T = total number of events.

Note: The total number of treatment-emergent AEs counts all treatment-emergent AEs for subjects. At each level of subject summarization, a subject is counted once if the subject reported one or more events. Percentages are based on the number of subjects within each cohort.

Adverse Events were coded using MedDRA, Version XX.X.

Source Data: Listing 16.2.7.1

<DIRECTORY PATH>PROGRAM NAME Executed: DDMMYYYY hh:mm

Prog Note:

1. AEs will be sorted alphabetically by SOC. Within each SOC, AEs will be sorted in decreasing frequency of Preferred Term, based on the total treatment column.

Table 14.3.1.2
Treatment-Emergent Adverse Events by Severity
Safety Set

System Organ Class Preferred Term	SB-318 1.00E+13 vg/kg (N=xxx)											
	Grade 1		Grade 2		Grade 3		Grade 4		Grade 5		Missing	
	n (%)	T	n (%)	T	n (%)	T	n (%)	T	n (%)	T	n (%)	T
NUMBER OF SUBJECTS WITH AT LEAST ONE TREATMENT-EMERGENT ADVERSE EVENT	xx (xx.x)	xx	xx (xx.x)	xx	xx (xx.x)	xx	xx (xx.x)	xx	xx (xx.x)	xx	xx (xx.x)	xx
SYSTEM ORGAN CLASS #1	xx (xx.x)	xx	xx (xx.x)	xx	xx (xx.x)	xx	xx (xx.x)	xx	xx (xx.x)	xx	xx (xx.x)	xx
PREFERRED TERM #1	xx (xx.x)	xx	xx (xx.x)	xx	xx (xx.x)	xx	xx (xx.x)	xx	xx (xx.x)	xx	xx (xx.x)	xx
PREFERRED TERM #2	xx (xx.x)	xx	xx (xx.x)	xx	xx (xx.x)	xx	xx (xx.x)	xx	xx (xx.x)	xx	xx (xx.x)	xx
...												

n = number of subjects experiencing the event. T = total number of events.

Note: GRADE 1=MILD, GRADE 2=MODERATE, GRADE 3=SEVERE, GRADE 4=POTENTIALLY LIFE THREATENING, GRADE 5=FATAL

The total number of treatment-emergent AEs counts all treatment-emergent AEs for subjects. At each level of subject summarization, a subject is counted once for the most severe event if the subject reported one or more events. Percentages are based on the number of subjects within each cohort.

Adverse Events were coded using MedDRA, Version XX.X.

Source Data: Listing 16.2.7.1

<DIRECTORY PATH>PROGRAM NAME Executed: DDMMYYYY hh:mm

Prog Note:

1. Following SB-318 1.00E+13 vg/kg, display SB-318 5.00E+13 vg/kg and Total in the next pages.

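### By-dose TEAE percentages and event counts can rest on unequal follow-up (12 months or less up to 36), and the AE tables do not show it

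*SAP*

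**What the plan says.** SAP 3.2.1 states: "The primary endpoint of this study is the incidence of treatment-emergent AE's (including SAEs"). SAP 8.1.1 defines a TEAE as "any adverse event with an onset date on or after the date of the SB-318 infusion through the last study visit", and Protocol 10.2 uses the same window, "from any time from administration of the study treatment through the last study visit". Neither sets a fixed cut-off.

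The last visit may fall at different times. The protocol synopsis plans about 3 months of screening "followed by 36 months for treatment and study follow-up", and Protocol 3.4 adds that "study subjects may participate in the LTFU Study after at least 12 months of follow-up" in this study. Protocol 6.9 then allows the End of Study visit at any point between Week 52 and the next scheduled visit. It also goes further: "Study participants who wish to enroll in the LTFU Study with less than 12 months of follow-up in this primary study may be considered" case by case, with no minimum stated.

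SAP 8.1.1 summarises AEs as counts and percentages of subjects. The shell for Table 14.3.1.1 adds T, the total number of events, and says "Percentages are based on the number of subjects within each cohort". The other AE shells, through Table 14.3.3.3, follow the same pattern. SAP 8 presents results separately by dose level and keeps every dosed subject in the analyses, including those who withdraw early.

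**The concern.** A percentage of subjects with an event grows with observation time, and so does a raw event count. If the subjects in one dose column left soon after Week 52 and those in another stayed to Month 36, the two columns would differ even at the same underlying risk. Nothing in the AE tables would tell the reader why.

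The plan has no safeguard in the summary tables: no subject-time, no rate, no common window, no by-period split and no table of follow-up duration. The SAP does not mention roll-over to the LTFU study. Table 14.1.1.1 offers only completed or early terminated, so it is unclear how a subject who rolls over at Month 12 is classed, or whether completed means 12 or 36 months.

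These columns carry the primary safety result, and they are small: 1 subject in Cohort 1 and 2 in each other cohort before any expansion. One subject's transfer date can change a column.

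**Working it through.** **The plan's own figures.** Sample size: 1 + 6 × 2 = 13 planned subjects, plus about 2 more in each of 7 cohorts (14), gives 27, as stated. Duration: 3 + 36 = 39 months, as stated. There is no power calculation to reproduce, and the documents give no AE rate, so the incidences below are assumptions shown over a range.

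**Observation time.** The standard roll-over point is 12 months and full follow-up is 36, a ratio of 36/12 = 3. For two 2-subject columns, one all at 12 months and the other all at 36, that is 24 against 72 person-months. Mixing early and late leavers within columns shrinks the contrast; transfer before Month 12 widens it.

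**Effect on the percentage.** Let p12 be the chance that a subject has a given event by Month 12, and f the share of the 36-month cumulative hazard that falls in the first 12 months. Then p36 = 1 − (1 − p12)^(1/f). A constant hazard has f = 1/3, so p36 = 1 − (1 − p12)³.

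| Share of hazard in Year 1 | p36 if p12 = 10% | p36 if p12 = 20% | p36 if p12 = 50% |
|---|---|---|---|
| All (f = 1) | 10% | 20% | 50% |
| 80% (f = 0.8) | 12.3% | 24.3% | 58.0% |
| Constant (f = 1/3) | 27.1% | 48.8% | 87.5% |

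For example, 1 − 0.8³ = 1 − 0.512 = 48.8%.

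**Effect on a 2-subject column.** The chance that at least one of two subjects is affected is 1 − (1 − p)². With p12 = 20% it is 36.0% at 12 months. At 36 months under a constant hazard it is 1 − 0.512² = 73.8%.

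**Effect on T.** Expected event counts scale as 1/f: unchanged if all events are early, 1/0.8 = 1.25-fold at f = 0.8, and 3-fold under a constant rate. At an assumed 1 event per subject-year, a 2-subject column expects 2 × 1 × 1 = 2 events over 12 months and 2 × 1 × 3 = 6 over 36.

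**What can be recovered.** Listing 16.2.1.1 prints each subject's completion or termination day counted from infusion, and Listing 16.2.7.1 prints each AE's start day. A reader can rebuild follow-up from these subject by subject. No table does so.

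**The case against.** - **The analysis is descriptive and the columns are tiny.** SAP 1 rules out hypothesis tests, the primary objective is safety and tolerability, and no between-dose contrast is specified. With 1 or 2 subjects in a column, no percentage can rank doses. This limits the importance of the point. It does not remove it, because the tables still set dose columns side by side, and a percentage over undisclosed, unequal follow-up describes them poorly.
- **Follow-up is already in the listings.** True, and so the fix should need little or no new data. It does not make the summary of the primary endpoint self-explanatory.
- **The main named risk is early.** Protocol 3.5 cites transaminitis at 2 to 9 weeks in previous AAV work, and the planned steroid taper runs about 20 weeks. For such events the distortion is small or nil. This stands, and it is why the size must be given as a range. It does not cover late events such as the malignancy and liver mass that the trial monitors.
- **Roll-over as a dose-linked bias.** A reader might infer that, because cohorts enrol in sequence, roll-over timing will differ systematically by dose and make some doses look safer. The documents do not support that: transfer is offered on the same terms to every subject, and nothing ties it to dose or calendar time.
- **Late events as lost.** A reader might also infer that events after roll-over go unrecorded. The protocol sets up the LTFU study for long-term safety monitoring. Such events leave this trial's tables, but the documents do not show that they go uncollected.

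**Conclusion.** The point holds as a reporting gap. The TEAE window ends at each subject's last visit, the protocol lets that visit fall anywhere from about Month 12 (or earlier) to Month 36, and the AE tables neither show nor adjust for the difference. Whether an imbalance will arise, and whether it would follow dose, the documents do not say.

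The size depends on when events occur. For a 12-month incidence of 20%, the comparison ranges from no difference, through 20% against about 24%, to 20% against 49% with a 3-fold difference in T. The last figures need a constant hazard and the extreme split between columns, so they should not be read as the expected effect. With a descriptive aim, very small columns and usable listings, this is an inexpensive improvement to the display and not a flaw that undermines the trial.

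**What to change.** In SAP 8.1.1 and the AE shells (Tables 14.3.1.1 to 14.3.3.3):

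1. Add total subject-years and the range of follow-up to each column header.
2. Add a version of the main TEAE table (14.3.1.1) and the serious TEAE table (14.3.2.1) limited to onset from infusion through Week 52, and name it as the display to use when dose columns are read side by side. Because earlier transfer and withdrawal are possible, footnote the subjects who left before Week 52.
3. Keep the whole-study tables, so that late events stay visible.
4. Treat events per subject-year beside T as optional: in a column of 1 or 2 subjects, one subject's repeated events determine the rate.
5. Show LTFU roll-over as its own category in Table 14.1.1.1 and Listing 16.2.1.1, and state whether it counts as completion.

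The change affects analysis and shells only. The listings already carry infusion, completion or termination, and AE onset dates; the sponsor should confirm that LTFU transfer is captured as a distinct reason for leaving. The downside is a few extra tables.

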## **10 SAFETY MONITORING AND ADVERSE EVENTS**

### **10.1 Definitions**

#### **10.1.1 Adverse Event**

An AE is any untoward medical occurrence in a patient or a clinical trial subject administered a medicinal product. An AE does not necessarily have a causal relationship with the administered treatment. The term can include any of the following events that develop or increase in severity during the course of this study:

- Any sign, symptom, or physical examination finding that worsens in nature, severity, or frequency compared to Baseline, whether thought to be related or unrelated to the condition under study.
- Any clinically significant laboratory abnormality or laboratory abnormality that requires medication or hospitalization.
- All reactions associated with the use of the study treatment, including those occurring as a result of an overdose, abuse, withdrawal phenomena, sensitivity, or toxicity to the study treatment.
- Concurrent illness.
- Injury or accident.

A pre-existing condition is one that is present prior to or at the start of the study, and is to be reported as part of the subject's medical history. It should be reported as an AE only if the frequency, intensity, or the character of the condition worsens during study participation.

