### **13.4 Primary Endpoint**

The primary endpoint of this study is the incidence of treatment-emergent AEs (including SAEs). Additional safety evaluations will include:

- Routine hematology, chemistry, and liver function laboratory tests, vital signs, physical exam, ECG, ECHO, and concomitant medications.
- Monitoring of chimerism in post-HSCT subjects.
- Cranial nerve exam and muscle strength testing.
- Serial AFP testing and MRI of liver to evaluate for liver mass.

Safety assessment will be performed on all subjects. All reported AEs will be coded to a standard set of terms using the Medical Dictionary for Regulatory Activities (MedDRA).

Treatment-emergent adverse events will be summarized overall and by treatment cohort. For each subject, the maximum reported severity of each adverse event will be used in the summaries by severity grade. In addition, all serious adverse events and AEs related to study treatment will be summarized.

Laboratory data will be summarized for each time-point at which specimens are collected. Change-from-Baseline values may be calculated for selected laboratory parameters. Shift-tables (Change-from-Baseline relative to the normal range) may be constructed for selected laboratory parameters.

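### With no worsening clause in the TEAE definition, an AE recorded before infusion whose grade rises after SB-318 can be missed from every TEAE table

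*SAP*

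**What the plan says.** The primary endpoint is TEAE incidence (Protocol 13.4, SAP 3.2.1), so the TEAE rule decides what the primary analysis counts.

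- **SAP 8.1.1** takes as a TEAE "any adverse event with an onset date on or after the date of the SB-318 infusion", up to the last study visit and regardless of causality.
- **Protocol 10.2** takes "any AE with an onset from any time from administration of the study treatment through the last study visit".
- **SAP 8.1.1 date rules** use the end date as well, but only under the headings for missing or partly missing dates. With a complete onset date, onset decides.
- **Collection** starts well before infusion. Protocol 10.2 states: "AEs will be monitored continuously during the study from the time that the subject has provided written informed consent".
- **The AE concept** in Protocol 10.1.1 is wider than the TEAE rule. It covers "any of the following events that develop or increase in severity during the course of this study", and its first listed item is "Any sign, symptom, or physical examination finding that worsens in nature, severity, or frequency compared to Baseline". A pre-existing condition goes to medical history and becomes an AE if it worsens during participation.
- **Laboratory results** (Protocol 10.3): a Grade 3 or 4 result that is worse than Baseline is reported as an AE, unless it belongs to a diagnosis already on the CRF.
- **Output**: all nine AE summary categories in SAP 8.1.1 are restricted to TEAEs. All AEs, treatment-emergent or not, are listed.

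**The concern.** An event that is mild before dosing and becomes severe afterwards is one that a first-in-human gene-transfer study should tabulate. The protocol's AE definition recognises worsening, but the TEAE rule that feeds the primary endpoint does not mention it.

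There is room for such events. Screening may take about 3 months (Protocol 6.1). Baseline falls within 21 days before infusion and includes a liver biopsy and a lumbar puncture unless contraindicated, with prednisone or equivalent from 2 days before infusion (Protocol 6.3, 9.30, 9.31). An AE that starts in this period can still be open at infusion.

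If it worsens later, whether it counts depends on how the site fills in the form. Two subjects with the same clinical course could then be tabulated differently. In cohorts planned at 1 or 2 subjects, one such difference changes a row visibly.

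**Working it through.** The plan gives no figure to reproduce: the sample size has no statistical basis (SAP 4.1) and no hypothesis is tested (SAP 1). The check is to apply the written rules case by case and then size one reclassified subject.

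**Step 1. Apply the rules to post-infusion worsening.**

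| Situation | What the documents provide | Counted as a TEAE? |
|---|---|---|
| Condition in medical history worsens | An AE under Protocol 10.1.1 | Yes, if dated at the worsening |
| Sign or symptom worse than Baseline, no AE record yet | An AE under Protocol 10.1.1 | Yes, if dated at the worsening |
| Grade 3 or 4 laboratory result worse than Baseline, no related diagnosis on the CRF | An AE under Protocol 10.3 | Yes, if dated at the worsening |
| The same, tied to a diagnosis recorded before infusion | Protocol 10.3 requires no separate AE | No, if only the old record exists |
| AE recorded between consent and infusion; site opens a new record | Permitted, not required | Yes |
| AE recorded between consent and infusion; site raises the grade on the old record | Permitted, not ruled out | No |
| Onset date missing, end date after infusion | SAP 8.1.1 date rules | Yes, assumed |

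The gap lies in the fourth and sixth rows. The last row shows an oddity: an ongoing event with no onset date is presumed treatment-emergent, while one with a known pre-infusion onset and documented worsening is not. The better-documented event gets the less cautious treatment.

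**Step 2. See whether another output recovers the event.** SAP 8.1.1 says that all AEs will be summarised by maximum severity, but the only severity shell, Table 14.3.1.2, is limited to TEAEs. The shell for Listing 16.2.7.1 would show the event, with one start date, one stop date and one severity per record. It has no date of grade change, so a reader could not tell whether the listed grade was reached before or after infusion.

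**Step 3. Size one reclassified subject.** The shift in a row is 100/n percentage points. Here n is the number of subjects in the column, and the subject is assumed to have no other qualifying event in that row. Planned cohort sizes are from Protocol 3.5: 1 + 6 × 2 = 13 subjects. With 2 more in each of 7 cohorts, 13 + 14 = 27, the stated maximum.

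| n | Shift (percentage points) |
|---|---|
| 1 (Cohort 1) | 100/1 = 100 |
| 2 (other cohorts as planned) | 100/2 = 50 |
| 4 (expanded cohort) | 100/4 = 25 |
| 13 (all planned) | 100/13 = 7.7 |
| 27 (maximum) | 100/27 = 3.7 |

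If the subject has another qualifying event in the row, the shift is 0.

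**The case against.** The strongest reply is that the protocol already treats worsening as an AE. Protocol 10.1.1 covers both worsening against Baseline and worsening of a pre-existing condition, and Protocol 10.3 covers severe laboratory worsening. A site that enters these as AEs dated at the worsening satisfies the onset rule. What is left is an AE entered between consent and infusion, still open at infusion, that worsens later and is updated on the old record. CRF completion guidance is not in the documents, and Protocol 6 refers to a Study Reference Manual that may deal with it. This stands, and it limits the point to events that can be missed. A reader might infer that any pre-infusion AE that worsens is excluded from the primary endpoint; the documents do not support that.

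It is also fair that the event is not lost from view. All AEs are listed, and with so few subjects the listings carry much of the safety reading. SAP 8.1.2 summarises change from baseline for the liver panel and gives shift tables for selected laboratory parameters. The SMC triggers in Protocol 11.5 and 12.3 and SAP 10 are written for AEs, SAEs, death and malignancy, so real-time oversight does not depend on the TEAE definition. This too stands, except that the listing cannot date the grade change.

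Finally, a reader might take 50 points as the effect on overall TEAE incidence. That holds only for a subject with no other TEAE, and follow-up lasts up to 36 months. The rows more likely to move are those by system organ class or preferred term, Grade 3 or greater, and serious.

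**Conclusion.** The point holds in limited form. For AEs with a complete onset date, neither the SAP nor the protocol counts worsening of an AE already on record. Such an event can be missed from every TEAE table if the site raises the grade on the existing record, and nothing in the documents requires a new one. Protocol and SAP agree with each other here; the weakness is in the rule they share.

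The size is 50 percentage points in the affected row of a 2-subject cohort and 100 in Cohort 1. This assumes that the row's denominator is the planned cohort size and that the subject has no other qualifying event in the row. The number of such events cannot be estimated from the documents and may be zero. The conclusion also assumes that no site instruction outside these documents settles the recording question. The change is worth making because it frees the primary endpoint from site recording habits, but subject protection during the trial does not turn on it.

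**What to change.** Three linked changes are needed:

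1. **Definition.** Add to SAP 8.1.1 and Protocol 10.2: *or any AE present before infusion that worsens in severity on or after infusion*. State that the comparison is with the grade at infusion. Say also whether worsening in nature or frequency, which Protocol 10.1.1 recognises, is meant to count.
2. **Recording.** State that such worsening is entered as a new AE with onset at the date of worsening, including where Protocol 10.3 would otherwise attach a laboratory result to an earlier diagnosis. Without this, the SAP sentence alone cannot be programmed, because the listing shell shows one severity per record. Flag only the new record as treatment-emergent, so that the event totals in the tables do not count it twice.
3. **Severity table.** Use the maximum grade reached on or after infusion, so that a peak before dosing is not shown as a post-dose grade.

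The text itself is a few sentences. The real cost is in the data: sites must supply a worsening date for AEs ongoing at infusion. The shells are dated 10 January 2022, so AEs already recorded before infusion would need a query or a review of source records. That is a small task at these cohort sizes.
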